#### 10.4.2 Factors Probably Affecting Safety

For adverse drug reactions reported in the observation period, the frequency of patient demographics (e.g., sex, age), details of treatment (e.g., status of Nesina, and status of concomitant medications) will be stratified.

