1.0 Definition of Terms and Handling of Laboratory/Measured Data

1.1 Definitions

Term	Definition
Nesina	Nesina tablet(s) is abbreviated as Nesina in this statistical analysis plan.
SOC	System Organ Class of MedDRA/J MedDRA/J version 20.1 is used for this document.
HLGT	High level group term of MedDRA/J
PT	Preferred term of MedDRA/J
LLT	Lowest level term of MedDRA/J
Registered patients	Patients whose registration was approved
Survey sheet collected patients	Patients whose survey sheets were collected
Survey sheet uncollected patients	Of the registered patients, patients whose survey sheets were uncollected.
Safety Analysis Set	Of the survey sheet collected patients, patients who were evaluated for safety analysis. For tabulation, the description of “total” means the Safety Analysis Set.
Not Safety Analysis Set	Of the survey sheet collected patients, patients who were excluded from safety analysis
Efficacy Analysis Set	Of the Safety Analysis Set, patients who were evaluated for efficacy analysis
Not Efficacy Analysis Set	Of the Safety Analysis Set, patients who were excluded from the efficacy analysis
First date of Nesina treatment	Of the start dates of the Nesina treatment period in patients, the earliest date is defined as the first date of Nesina treatment.
Last date of Nesina treatment	Of the last dates of the Nesina treatment in patients, the latest date is defined as the last date of Nesina treatment. If Nesina treatment is continued and the year, month, and date of the continued treatment period are specified, the year, month, and date of the continued treatment period are defined as the last date of Nesina treatment. If the data for the year, month, and date of the continued treatment period are missing, the following date is defined as the last date of Nesina treatment. (1) First date of Nesina treatment + 1 year (same month and date) for continued treatment of Nesina. (2) Latest date at which the following examinations/observations will be performed for the not-continued treatment of Nesina: 
 • [Date of examinations/ observations] 
 • Compliance with Nesina treatment

Term	Definition
	
 • Compliance with diet/exercise therapy • Laboratory tests • Body weight • Waist circumference • Pulse rate • Blood pressure • Electrocardiography • Tests for coronary atherosclerosis and arteriosclerosis

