	
If the onset month and date of an adverse event (or adverse drug reaction, etc.) is unknown, calculate the onset month and date as January 1. However, if the start month and date of Nesina treatment are same as the onset month and date of an adverse event (or adverse drug reaction, etc.), the onset period will be calculated as the start date of Nesina treatment.
 
For unknown onset date of adverse events (or adverse drug reactions, etc.), the onset period will be calculated as 1 day. However, if the start month and date of Nesina treatment are same as the onset month and date of adverse events (or adverse drug reactions, etc.), the onset period will be calculated as the start date of Nesina treatment.

Treatment group	
Overall: Total patients who will be treated with combination therapy with insulin preparation, rapid-acting insulin secretagogues, SGLT-2 inhibitors, and other (all are defined below)
 
Combination with insulin preparation: Patients who will be treated with insulin preparation within 3 months prior to Nesina treatment and during Nesina treatment (including at the start of Nesina treatment) and not treated with rapid-acting insulin secretagogues or SGLT-2 inhibitors
 
Combination with rapid-acting insulin secretagogues: Patients who will be treated with rapid-acting insulin secretagogues within 3 months prior to Nesina treatment and during Nesina treatment (including at the start of Nesina treatment) and not treated with insulin preparation or SGLT-2 inhibitors
 
Combination with SGLT-2 inhibitors: Patients who will be treated with SGLT-2 inhibitors within 3 months prior to Nesina treatment and during Nesina treatment (including at the start of Nesina treatment) and not treated with insulin preparation or rapid-acting insulin secretagogues
 
Other: Patients who will not be treated with combination therapy with insulin preparation, rapid-acting insulin secretagogues, or SGLT-2 inhibitors

Patients with diabetic complication	Patients with any of the following complications: diabetic nephropathy, diabetic retinopathy, or diabetic neuropathy.
Patients with diabetic nephropathy	Patients with complication of PT Code 10012660 (diabetic end stage renal disease) or 10061835 (diabetic nephropathy).
Patients with diabetic retinopathy	Patients with complication of PT Code 10012688 (diabetic retinal oedema) or 10012689 (diabetic retinopathy).

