1.4 Level of Significance and Confidence Coefficient

Two-sided 5%, two-sided 95%.

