5.4 Patient Demographics and Frequency of Adverse Drug Reactions / Infections by Treatment

5.4.1 Patients demographics and Frequency of Adverse Drug Reactions / Infections by Treatment

(1) Patients to be tabulated and analyzed

Safety Analysis Set

(2) Details of tabulation and analysis

Each parameter will be categorized by the categories described below to tabulate the percent of patients with adverse drug reactions, etc.

The Fischer exact test will be used for parameters without rank data. The Mann-Whitney U test will be used for parameters with rank data. (The tests will be used for parameters with asterisk [*].)

Total patients and patients who are taking concomitant insulin preparation, rapid-acting insulin secretagogues, SGLT-2 inhibitors, or other drugs will be tabulated.

Parameter	Category
Sex*	Male, Female
Age*	< 65 years, ≥ 65 years
	< 75 years, ≥ 75 years
Concurrent liver disorder*	No, Yes
Severity of hepatic	Normal, Grades 1, 2, and 3, or Unknown

Parameter	Category
impairment*	
Concurrent renal disorder*	No, Yes
Severity of renal impairment* (eGFR)	Normal + Mild, Moderate + Severe, or Unknown
Severity of renal impairment* (serum creatinine)	Normal + Mild, Moderate + Severe, or Unknown
Concurrent heart disease*	No, Yes
Details of concurrent heart disease (overlapped)	Cardiac failure, myocardial infarction, or angina pectoris
Concurrent cardiac failure*	No, Yes
Severity classification of cardiac failure (NYHA classification)*	Classes NYHA I, NYHA II, NYHA III, and NYHA IV, or Unknown
Concurrent stroke-related disease*	No, Yes, or Unknown
Mean daily dose of Nesina	> 25 mg, 25 to >12.5 mg, 12.5 to > 6.25 mg, or ≤ 6.25 mg
Administration of concomitant medication (diabetic drug)	No, Yes
Concomitant medications (diabetic drugs) (overlapped)	α-glucosidase inhibitors, thiazolidines, sulfonylureas, biguanides, rapid-acting insulin secretagogues, or insulin preparations, DPP-4 inhibitors, GLP-1 receptor agonists, SGLT-2 inhibitors, combination of diabetic drugs, or other diabetic drugs
Administration of concomitant medication (protease drug)*	No, Yes, or Unknown
Administration of	No, Yes, or Unknown

Parameter	Category
concomitant medication (combined with renal excretory drug)*	

(3) Number of tables and figures

Table 5.4.1-1

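### SAP 5.4.1 plans no test of ADR risk factors stratified by background drug, so a test on the pooled Total can mix a background-drug difference with an age, renal or heart-disease effect

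*SAP*

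**What the plan says.** Protocol 10.4.2 asks for a stratified tabulation and names no test: "For adverse drug reactions reported in the observation period, the frequency of patient demographics" and of treatment details, including concomitant medication, is to be broken down.

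SAP 5.4.1 adds tests. "The Fischer exact test will be used for parameters without rank data"; "The Mann-Whitney U test will be used for parameters with rank data". As to which rows: "The tests will be used for parameters with asterisk". The starred rows are sex, age, liver disorder and hepatic severity, renal disorder and the two renal severity scales, heart disease, cardiac failure and NYHA class, stroke-related disease, protease drug and renal excretory drug. The rows for concomitant diabetic drugs carry no asterisk. SAP 1.4 sets a two-sided 5% level.

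On columns, 5.4.1 says: "Total patients and patients who are taking concomitant insulin preparation, rapid-acting insulin secretagogues, SGLT-2 inhibitors, or other drugs will be tabulated". SAP 1.1 adds: "For tabulation, the description of “total” means the Safety Analysis Set". It describes the overall group as "Overall: Total patients who will be treated with combination therapy with insulin preparation, rapid-acting insulin secretagogues, SGLT-2 inhibitors, and other". So Total pools all background drugs, and every factor is also shown within each treatment group. The section does not say in which columns the tests are run. No CMH test, stratified exact test or regression model for ADRs appears anywhere in the SAP.

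**The concern.** The survey combines Nesina with classes as different as insulin and SGLT-2 inhibitors, and SAP 1.2 lists hypoglycemia first among the important identified risks. It is reasonable to expect ADR risk to differ by background drug, and age, renal function and heart disease to differ as well. Where both differ, an unadjusted test on Total attributes part of the drug difference to the patient factor. A factor with no effect within any group can reach p < 0.05, and a real one can be hidden if the imbalance runs the other way.

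The group columns are free of this bias, but each holds only part of the events. The reader would have one pooled p-value and several weak ones, with no rule for weighing them. At stake is which factors the survey reports as affecting safety.

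**Working it through.** The plan has no figure to reproduce: Protocol 3.2 says that the 1,000 participants were not chosen on statistical grounds. The check is therefore a simulation on assumed inputs.

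**From the documents.** N = 1,000 (Protocol 3.1); about 58% elderly (Protocol 3.2, taken from surveys of other background therapies); two-sided 5% (SAP 1.4).

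**Assumed.** Group sizes 400 insulin, 250 secretagogue, 250 SGLT-2, 100 other. ADR risk depends on group only, so there is no age effect within any group. Two age imbalances, as the share aged 65 or over in that order: mild 63/63/43/58%, strong 70/65/30/58%.

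**Why pooling biases.** Take the strong imbalance with ADR risks 12/5/3/5%.
- Aged 65 or over, 280/162/75/58 = 575 patients: expected ADRs 33.6 + 8.1 + 2.25 + 2.9 = 46.85, or 8.15%.
- Under 65, 120/88/175/42 = 425 patients: 14.4 + 4.4 + 5.25 + 2.1 = 26.15, or 6.15%.
- Pooled odds ratio (0.0815/0.9185) / (0.0615/0.9385) = 1.35, although it is 1.00 within every group.

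**Tests compared.** Fisher exact on the pooled 2×2 table, against CMH by group without continuity correction: X² = [Σ(a − E)]² / ΣV, with E = m·n1/n and V = n1·n0·m·(n − m) / [n²(n − 1)], referred to chi-square on 1 df. Here a is the number of ADRs among the n1 older patients of a group, m the group's ADRs, and n0 its younger patients. There were 20,000 runs per setting.

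| Age imbalance | ADR risk by group | Pooled OR | Fisher rejects | CMH rejects |
|---|---|---|---|---|
| none | 3% in all | 1.00 | 3.9% | 5.2% |
| none | 12/5/3/5% | 1.00 | 4.1% | 4.9% |
| mild | 3/1.5/1/1.5% | 1.11 | 4.2% | 5.0% |
| mild | 6/3/2/3% | 1.12 | 5.1% | 5.1% |
| mild | 12/5/3/5% | 1.15 | 7.5% | 5.1% |
| strong | 3% in all | 1.00 | 3.7% | 4.8% |
| strong | 3/1.5/1/1.5% | 1.27 | 6.0% | 5.1% |
| strong | 6/3/2/3% | 1.27 | 9.0% | 4.9% |
| strong | 12/5/3/5% | 1.35 | 20.6% | 5.2% |

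Inflation needs both conditions: with equal ADR risk, or with an equal age mix, there is none. Fisher is conservative, so its unbiased reference here is about 4%. With the continuity correction CMH rejects in 2.6% to 3.8%.

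**A renal factor.** A second assumed set has groups of 450/250/250/50, 65/65/38/58% aged 65 or over, and renal impairment in 25/15/4/15%. At ADR 8/5/2/3%, Fisher rejects in about 9% (age) and 11% (renal), with spurious risk ratios of 1.20 and 1.29; CMH gives 5.0% and 4.2%. At 3/2/1/1.5% Fisher gives 5.1% and 6.7%. At 5/4/3/4% there is no material inflation (5.0% and 5.4%).

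**Power within a group column.** For 3% v 6% with a 42/58 split, power = Φ[(0.03 − 1.96·SE0)/SE1], SE0 being the pooled and SE1 the unpooled standard error.
- n = 1,000: SE0 = 0.01362, SE1 = 0.01291, power 60%. Both errors scale with 1/√n.
- n = 400: 28%. n = 250: 18%. n = 100: 9%.

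**The case against.** The other side has several good points.

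- A reader might infer that the plan ignores background drug. It does not: 5.4.1 itself repeats the table within each treatment group, which meets Protocol 10.4.2. Only a combined stratified test is absent.
- A reader might also infer that the SAP orders tests on Total and will declare confounded factors significant. The columns tested are not named; Total is an inference, though a fair one, since it is the first column listed after the tests. No decision rule is attached to the p-values, and the survey's size has no statistical basis. These are exploratory results.
- The larger inflation figures need a fourfold ADR gradient between insulin and SGLT-2 patients and an age gap of 40 points (or 27 points in the second set). Milder assumptions give little or none.
- Stratifying by the SAP 1.1 treatment group would be unsound. Membership depends on drugs used during Nesina treatment, so a change of drug after an event such as hypoglycemia can move a patient between strata. Patients on two or three of the named classes fit none of the combination groups, nor Other, yet belong to the Safety Analysis Set. The simulation fixes group before any ADR and cannot show this bias.
- Stratifying by drug alone leaves age, renal function and heart disease confounded with one another.

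All of this stands. It limits the size of the point and shapes the fix; it does not supply the missing combined test. A 5% level and named tests invite readers to treat small p-values as risk factors.

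**Conclusion.** The point holds in a limited form. SAP 5.4.1 offers unadjusted one-factor tests and within-group percentages, but nothing that combines the groups while conditioning on background drug, so any Total p-value can carry a background-drug difference. Over the assumed settings the pooled false-positive rate runs from about 4-5%, which is no inflation, to about 21%, with CMH near 5% throughout. Where the actual survey falls cannot be told from the documents: ADR rates, group sizes and factor mixes by group are all assumptions. The documents do not support saying that the Total tests are biased in fact, or that the plan fails to stratify. They support saying that the plan leaves this bias unchecked when a check is cheap. It is a recommended improvement to an exploratory table.

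One matter comes first: SAP 1.1 defines ADRs as events the investigator judged not related to Nesina. That must be reconciled before any result in 5.4.1 can be read.

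**What to change.** In SAP 5.4.1:

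1. State which columns are tested. Keep the Fisher and Mann-Whitney p-values for Total, labelled unadjusted and exploratory.
2. Beside them print a test stratified by background drug class at the start of Nesina treatment: CMH (exact if sparse) for two-level and nominal factors, van Elteren for ranked factors. For two-level factors add the Mantel-Haenszel common risk or odds ratio with 95% CI.
3. Define the strata from drug use at the start of treatment, not from the SAP 1.1 treatment group: insulin only, secretagogue only, SGLT-2 inhibitor only, more than one of these, none of these. Protocol 9.2.3 already collects drug names and administration periods, and SAP 1.1 already has the class codes.

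Cost: SAP wording, one derived variable and some extra programming. The stratified test works best when the effect is common across strata; the group columns let the reader check that roughly. Confounding among age, renal function and heart disease remains, and a footnote should say so.

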5.5 Occurrence of Adverse Drug Reactions / Infections by Age

(1) Patients to be tabulated and analyzed

Safety Analysis Set

(2) Details of tabulation and analysis

Age will be classified into < 65 years, ≥ 65 years and < 75 years, and ≥ 75 years for tabulation of type of adverse drug reactions, etc.

The method for tabulation of adverse drug reactions, etc. is same as that described in Section 5.1.

Total patients and patients who are taking concomitant insulin preparation, rapid-acting insulin secretagogues, SGLT-2 inhibitors, or other drugs will be tabulated.

(3) Number of tables and figures

Tables 5.5-1 to 5.5-2

5.6 Occurrence of Adverse Drug Reactions / Infections by Sex

(1) Patients to be tabulated and analyzed

Safety Analysis Set

(2) Details of tabulation and analysis

Sex will be classified into male or female for tabulation of type of adverse drug reactions, etc.

The method for tabulation of adverse drug reactions, etc. is same as that described in Section 5.1.

Total patients and patients who are taking concomitant insulin preparation, rapid-acting insulin secretagogues, SGLT-2 inhibitors, or other drugs will be tabulated.

(3) Number of tables and figures

Table 5.6-1

5.7 Occurrence of Adverse Drug Reactions / Infections by Liver Disorder

(1) Patients to be tabulated and analyzed

Safety Analysis Set

(2) Details of tabulation and analysis

Concurrent liver disorder will be classified into yes or no for tabulation of type of adverse drug reactions, etc.

The method for tabulation of adverse drug reactions, etc. is same as that described in Section 5.1.

Total patients and patients who are taking concomitant insulin preparation, rapid-acting insulin secretagogues, SGLT-2 inhibitors, or other drugs will be tabulated.

- (3) Number of tables and figures

Table 5.7-1

5.8 Occurrence of Adverse Drug Reactions / Infections by Liver Impairment

- (1) Patients to be tabulated and analyzed

Safety Analysis Set

- (2) Details of tabulation and analysis

Severity of liver impairment will be classified into Grade 1, 2, or 3 or unknown for tabulation of type of adverse drug reactions, etc.

The method for tabulation of adverse drug reactions, etc. is same as that described in Section 5.1.

Total patients and patients who are taking concomitant insulin preparation, rapid-acting insulin secretagogues, SGLT-2 inhibitors, or other drugs will be tabulated.

- (3) Number of tables and figures

Table 5.8-1

5.9 Occurrence of Adverse Drug Reactions / Infections by Presence of Concurrent Renal Disorder

- (1) Patients to be tabulated and analyzed

Safety Analysis Set

- (2) Details of tabulation and analysis

Concurrent renal disorder will be classified into yes or no for tabulation of type of adverse drug reactions, etc.

The method for tabulation of adverse drug reactions, etc. is same as that described in Section 5.1.

Total patients and patients who are taking concomitant insulin preparation, rapid-acting insulin secretagogues, SGLT-2 inhibitors, or other drugs will be tabulated.

- (3) Number of tables and figures

Table 5.9-1

5.10 Occurrence of Adverse Drug Reactions / Infections by Severity of Renal Impairment

- (4) Patients to be tabulated and analyzed

Safety Analysis Set

(5) Details of tabulation and analysis

Severity of renal impairment will be classified into normal + mild, moderate + severe, or unknown, according to the criteria for the severity of renal impairment (eGFR and serum creatinine) for tabulation of type of adverse drug reactions, etc.

The method for tabulation of adverse drug reactions, etc. is same as that described in Section 5.1.

Total patients and patients who are taking concomitant insulin preparation, rapid-acting insulin secretagogues, SGLT-2 inhibitors, or other drugs will be tabulated.

(6) Number of tables and figures

Tables 5.10-1 and 5.10-2

5.11 Occurrence of Adverse Drug Reactions / Infections by Presence of Concurrent Heart Disease

(1) Patients to be tabulated and analyzed

Safety Analysis Set

(2) Details of tabulation and analysis

Concurrent heart disease will be classified into yes or no for tabulation of type of adverse drug reactions, etc.

The method for tabulation of adverse drug reactions, etc. is same as that described in Section 5.1.

Total patients and patients who are taking concomitant insulin preparation, rapid-acting insulin secretagogues, SGLT-2 inhibitors, or other drugs will be tabulated.

(3) Number of tables and figures

Table 5.11-1

5.12 Occurrence of Adverse Drug Reactions / Infections by Presence of Concurrent Heart Failure

(1) Patients to be tabulated and analyzed

Safety Analysis Set

(2) Details of tabulation and analysis

Concurrent heart failure will be classified into yes or no for tabulation of type of adverse drug reactions, etc.

The method for tabulation of adverse drug reactions, etc. is same as that described in Section 5.1.

Total patients and patients who are taking concomitant insulin preparation, rapid-acting insulin secretagogues, SGLT-2 inhibitors, or other drugs will be tabulated.

(3) Number of tables and figures

Table 5.12-1

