Patients with diabetic neuropathy	Patients with complication of PT Code 10012645 (diabetic autonomic neuropathy), 10012676 (diabetic mononeuropathy), or 10012680 (diabetic

Term	Definition
	neuropathy).
Patients with concurrent hypertension	Patients with concurrent disease of the Standardised MedDRA Query (hereinafter SMQ) Code 20000147 (hypertension (SMQ) narrow).
Patients with concurrent dyslipidemia	Patients with concurrent disease of the SMQ Code 20000026 (dyslipidaemia (SMQ) narrow).
Patients with concurrent hyperuricemia	Patients with concurrent disease of the PT code meeting the Takeda MedDRA Query 20.1 (hereinafter, TMQ 20.1) (blood uric acid increased).
Patients with concurrent liver disorder	Patients with concurrent disease of the SMQ Code 20000005 (hepatic disorders (narrow).
Patients with concurrent hepatic steatosis	Patients with concurrent disease of the PT Code 10019708 (hepatic steatosis).
Patients with concurrent alcoholic hepatitis	Patients with concurrent disease of the PT Code 10019728 (hepatitis alcoholic).
Patients with concurrent chronic hepatitis	Patients with concurrent disease of the PT Code 10008909 (chronic hepatitis).
Patients with concurrent hepatic cirrhosis	Patients with concurrent disease of the PT Code 10019641 (hepatic cirrhosis).
Patients with concurrent renal disorder	Patients with concurrent disease of the TMQ 20.1 (renal disease).
Patients with concurrent nephrotic syndrome	Patients with concurrent disease of the PT Code 10029164 (nephrotic syndrome).
Patients with concurrent glomerulonephritis	Patients with concurrent disease of the PT Code 10018364 (glomerulonephritis) or the PT Code 10018367 (glomerulonephritis chronic).
Patients with concurrent chronic renal failure	Patients with concurrent disease of the PT Code 10064848 (chronic kidney disease) or the PT Code 10038435 (renal failure).
Patients with concurrent heart disease	Patients with concurrent disease of the SOC Code 10007541 (cardiac disorders).
Patients with concurrent cardiac failure	Patients with concurrent disease of the SMQ Code 20000004 (cardiac failure (SMQ) narrow).
Patients with concurrent myocardial infarction	Patients with concurrent disease of the SMQ Code 20000047 (myocardial infarction (SMQ) narrow).

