Severity of hepatic impairment	
Severity of hepatic impairment will be assessed using AST or ALT at the start of Nesina treatment. Severity will be assessed using the categories described below, and the higher grade of AST or ALT will be used for analysis.
 
Normal: < 50 IU/L
 
Grade 1: ≥ 50 IU/L and < 100 IU/L
 
Grade 2: ≥ 100 IU/L and < 500 IU/L
 
Grade 3: ≥ 500 IU/L
 
Quoted from the Standards for Classification of Serious Adverse Drug Reactions due to Drug Products notified by the director of Pharmaceuticals and Chemicals Safety Division, Pharmaceutical Affairs Bureau, the Ministry of Health and Welfare (No. 80 notification of Pharmaceuticals and Chemicals Safety Division, Pharmaceutical Affairs Bureau: June 29, 1992).

Severity of renal impairment (eGFR)	
eGFR* will be calculated based on age and serum creatinine at the start of Nesina treatment to assess the severity according to the categories described below. For unknown serum creatinine and age at the start of Nesina treatment, indicate as unknown. Indicate to one decimal place rounded from two decimals.
 
Normal: ≥ 90 mL/min/1.73 m²
 
Mild: ≥ 60 mL/min/1.73 m² and < 90 mL/min/1.73 m²
 
Moderate: ≥ 30 mL/min/1.73 m² and < 60 mL/min/1.73 m²
 
Severe: < 30 mL/min/1.73 m²
 
*eGFR = 194 × Cr^{-1.094} × age (year)^{-0.287} (×0.739 for females)

Term	Definition
	Cr: Serum creatinine at the start of Nesina treatment. For serum Cr, indicate to two decimal places. Quoted from the Clinical Practice Guide for CKD, edited by the Japanese Society of Nephrology.
Severity of renal impairment (serum creatinine)	Severity will be assessed based on serum creatinine at the start of Nesina treatment and according to the following categories: Normal + Mild: Males: ≤ 1.4 mg/dL, Females: ≤ 1.2 mg/dL Moderate: Males: > 1.4 mg/dL to ≤ 2.4 mg/dL, Females: > 1.2 mg/dL to ≤ 2.0 mg/dL Severe: Males: > 2.4 mg/dL, Females: > 2.0 mg/dL For undescribed serum creatinine level at the start of Nesina treatment, indicate as unknown.

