3.0 Patient Demographics

(1) Patients to be tabulated and analyzed

Safety Analysis Set

(2) Details of tabulation and analysis

Each parameter will be classified by the categories described below to tabulate the number of patients and frequency.

Total patients and patients who are taking concomitant insulin preparation, rapid-acting insulin secretagogues, SGLT-2 inhibitors, or other drugs will be tabulated.

Parameter	Category
Sex	Male, Female
Age	Summary statistics
	< 65 years, ≥ 65 years
	< 75 years, ≥ 75 years
	< 20 years, 20 to 29 years, 30 to 39 years, 40 to 49 years, 50 to 59 years, 60 to 69 years, 70 to 79 years, ≥ 80 years
Disease duration of type 2 diabetes mellitus (year)	Summary statistics
	< 2 years, 2 to < 5 years, 5 to < 10 years, ≥ 10 years, Unknown
Height	Summary statistics
Category of clinical practice	Outpatient, Inpatient
Pregnancy (only females)	No, Yes
Severity of renal impairment	Normal, Mild, Moderate, Severe
	Normal + Mild, Moderate + Severe
Concurrent disease	No, Yes
Diabetic complication	No, Yes
Details of diabetic complication (overlapped)	Diabetic nephropathy, diabetic retinopathy, diabetic neuropathy For the proportion, the number of patients with diabetic complication will be denominator.
Concurrent hypertension	No, Yes
Concurrent dyslipidemia	No, Yes
Concurrent hyperuricemia	No, Yes
Concurrent liver disorder	No, Yes

Parameter	Category
Details of concurrent liver disorder (overlapped)	Hepatic steatosis, alcoholic hepatitis, chronic hepatitis, hepatic cirrhosis, or other For the proportion, the number of with concurrent liver disorder will be denominator.
Severity of hepatic impairment	Normal, Grades 1, 2, and 3, or Unknown
Concurrent renal disorder	No, Yes
Details of concurrent renal disorder (overlapped)	Nephrotic syndrome, glomerulonephritis, chronic glomerulonephritis, other For the proportion, the number of with concurrent renal disorder will be denominator.
Severity of renal impairment (eGFR)	Normal, Mild, Moderate, Severe, or Unknown
	Normal + Mild, Moderate + Severe, or Unknown
Severity of renal impairment (serum creatinine)	Normal, Mild, Moderate, Severe, or Unknown
	Normal + Mild, Moderate + Severe, or Unknown
Concurrent heart disease	No, Yes
Details of concurrent heart disease (overlapped)	Cardiac failure, myocardial infarction, angina pectoris, other For the proportion, the number of with concurrent heart disease will be denominator.
Concurrent cardiac failure	No, Yes

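### SAP 5.4.1 and 5.10 pool moderate with severe renal impairment, so no planned table gives an ADR rate for the severe class that SAP 1.1 defines

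*SAP*

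**What the plan says.** All references are to the current SAP, the first of the three versions in the file. The two superseded versions pool in the same way.

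- **Definitions (SAP 1.1).** eGFR has four classes: normal, mild, moderate and severe. The last is "Severe: < 30 mL/min/1.73 m²". Serum creatinine has three, with normal and mild joined. Its last is "Severe: Males: > 2.4 mg/dL, Females: > 2.0 mg/dL".
- **Baseline (SAP 3.0).** Table 3.0-1 counts patients in each of the four eGFR classes. It holds no ADR data.
- **ADR frequency (SAP 5.4.1).** For both renal scales the categories are "Normal + Mild, Moderate + Severe, or Unknown". Both rows carry an asterisk, and "The tests will be used for parameters with asterisk".
- **ADRs by type (SAP 5.10).** Tables 5.10-1 and 5.10-2 use the same three groups: "Severity of renal impairment will be classified into normal + mild, moderate + severe, or unknown".
- **The other renal ADR table (SAP 5.9).** This has no severity split: "Concurrent renal disorder will be classified into yes or no for tabulation of type of adverse drug reactions, etc".
- **Detail of renal disorder (SAP 3.0).** The listed categories are "Nephrotic syndrome, glomerulonephritis, chronic glomerulonephritis, other".

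The Protocol asks for less. Section 10.6 says that safety and efficacy will be stratified for patients with renal impairment and mentions no severity classes. Section 5.0 refers renal patients to the package insert for dosing. Section 3.2 expects about 150 renal-impairment patients among 1,000 and says that the sample size has no statistical basis.

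**The concern.** The section headed as ADRs by severity of renal impairment cannot tell moderate from severe. A reader of the report would learn from Table 3.0-1 how many severe patients (by eGFR) were surveyed, but would find no ADR figure for them. If ADRs were more frequent only in severe impairment, the excess would be averaged over a class that is probably mostly moderate, and what remained could not be attributed to either class.

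The SAP gives no reason for the pooling, and its treatment of other organ systems differs. Table 5.4.1-1 keeps hepatic Grades 1 to 3 (Grade 3 starts at 500 IU/L) and NYHA I to IV as separate classes, as do SAP 5.8 and 5.13. Those classes may be sparse too.

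**Working it through.** **1. Which outputs cross ADRs with renal function**

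| SAP section | Renal grouping | Severe shown alone? |
|---|---|---|
| 3.0 (counts only) | four eGFR classes | yes, but no ADR data |
| 5.4.1 (tested) | two pooled classes and unknown, both scales | no |
| 5.9 | renal disorder yes or no | no |
| 5.10 | two pooled classes and unknown, both scales | no |

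The gap is complete: no row of any planned ADR table is the severe class.

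**2. The plan's own figure**

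Protocol 3.2 gives 15.1% renal impairment in the past survey and plans 1,000 participants: 1,000 × 0.151 = 151, which agrees with its approximate 150.

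**3. Dilution**

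Assumptions, none of them in the documents: all 150 patients fall in the moderate + severe class; a share s of them is severe; the ADR rate is 20% in severe and 5% in everyone else.

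Pooled rate = s × 20% + (1 − s) × 5%, so the pooled excess is s × 15 percentage points.

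| Severe patients of 150 | Pooled rate | Ratio to 5% |
|---|---|---|
| 8 (about 5%) | (8 × 0.20 + 142 × 0.05) / 150 = 5.8% | 1.16 |
| 15 (10%) | 0.1 × 20% + 0.9 × 5% = 6.5% | 1.3 |
| 30 (20%) | 0.2 × 20% + 0.8 × 5% = 8.0% | 1.6 |
| 45 (30%) | 0.3 × 20% + 0.7 × 5% = 9.5% | 1.9 |

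The true ratio is 4 in every row. Comparing 150 pooled patients with 850 normal + mild patients, a two-sided 5% Fisher exact test has power of about 6%, 11%, 29% and 52% in the four rows.

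**4. Would finer classes give a better test?**

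This was checked by simulating surveys of 1,000 patients, 151 of them moderate or severe, 15 or 30 of those severe, and normal assumed to be 30% of the rest.

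- *Risk rising through all four classes (3, 5, 7, 12%).* Power is 34-42% for two-class Fisher, 38-49% for two-class Mann-Whitney, 39-50% for three-class Mann-Whitney (normal + mild, moderate, severe) and 54-62% for four-class Mann-Whitney. Splitting severe from moderate adds only about 1-2 points. The rest comes from changing the test and from splitting normal from mild.
- *Risk raised only in severe (5, 5, 5, 20%).* Power is about 10-30% for pooled Fisher and about 10-23% for the four-class rank test, which is no better and may be slightly worse.

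**5. What a separate severe row could show**

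With 0 events in 15 patients the exact upper 95% limit is 1 − 0.025^(1/15) = 21.8%. With 3 events in 15 (20%) the exact 95% interval is 4.3% to 48.1%. These are wide, but they are information about the class that the plan would not otherwise report.

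**6. The renal list in SAP 3.0**

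SAP 1.1 already places chronic glomerulonephritis (PT 10018367) within glomerulonephritis. It also defines a chronic renal failure group from the PT codes for chronic kidney disease and renal failure. The 3.0 row lists chronic glomerulonephritis as a further category and never uses the chronic renal failure group.

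**The case against.** Much of the opposing case stands.

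- **No protocol breach.** Protocol 10.6 asks only for stratification by renal impairment, and SAP 5.9 and 5.10 provide it. The documents do not show a broken promise.
- **The data are not lost.** Creatinine is collected, the eGFR classes are derived and counted, and Protocol 14.2 provides for investigation if a safety question arises. What is missing is a pre-specified row.
- **A severe-only signal is not bound to stay hidden.** A reader might infer that it could never surface. That goes too far: with a 30% severe share the pooled Fisher test has about 52% power under the rates above. With a 10% base rate, a four-fold risk and the same share, power reaches 85% (normal approximation). What the pooled table cannot do is attribute an excess to the severe class.
- **Power is a poor argument for the change.** A reader might expect finer classes to give a stronger test. Step 4 shows that the four-class rank test does not help when only severe patients are at risk. A direct comparison of severe with normal + mild would do better under the assumptions of step 3 (Fisher power about 54% with 15 severe patients), but the SAP does not plan that contrast and it is not proposed here.
- **Cells will be small**, above all where 5.10 splits by treatment group and preferred term. The SAP accepts separate hepatic and NYHA classes in comparable tables, so this calls for showing counts and intervals. Whether sparseness was the sponsor's reason cannot be known.

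Nor do the documents say that severe impairment is the class of greatest concern. The point rests only on the SAP defining the class and then not reporting ADRs for it.

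**Conclusion.** The point holds as a reporting gap that is cheap to close. On both renal scales, every ADR table and test by renal severity merges moderate with severe, so no planned output gives the severe-class rate. If 10-20% of the pooled class is severe, a 15-point severe-only excess shrinks to 1.5-3.0 points.

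That size depends on the assumed severe share, the assumed ADR rates and the equating of the past survey's renal impairment with moderate + severe. The documents do not define the past survey's term. The absence of a severe row depends on none of these.

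The benefit of the change is descriptive. It should not be presented as a gain in power or as the repair of a conflict with the Protocol.

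The slip in SAP 3.0 is secondary: it affects a demographics row and no ADR analysis. Patients with chronic kidney disease or renal failure would presumably be counted under the residual category, but that depends on the sponsor's renal disease query, whose contents are not given.

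**What to change.** 1. In Tables 5.4.1-1, 5.10-1 and 5.10-2, show eGFR as normal, mild, moderate, severe and unknown, and creatinine as normal + mild, moderate, severe and unknown. The creatinine grouping follows SAP 1.1, which defines no boundary between normal and mild on that scale.
2. Print the number of patients in each class and use it as the denominator. The percentage formula in SAP 1.1 divides by the Safety Analysis Set and states no subgroup denominator.
3. In Table 5.4.1-1, add exact 95% confidence intervals for the class rates.
4. Keep the planned two-class split and its test as an extra row. No new test is needed.
5. In the SAP 3.0 row on details of concurrent renal disorder, replace chronic glomerulonephritis with the chronic renal failure group defined in SAP 1.1.

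The cost is SAP wording and some extra table columns, with no new data. The drawback is sparse severe cells, which the printed denominators and intervals make plain.
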